### Interventions and Duration

Primary care clinics within each of the two participating ACOs will be randomized to either the intervention or control arms of the study. Prior to random assignment, we will stratify practices based on high versus low historic prescribing rates, with the cut-point for including a clinic in the study based on the distribution of overall rates for all 3 therapeutic classes using data for 2019-2020. A primary care clinician from each clinic selected for the trial in the intervention arm (n=30 across the two ACOs) will be recruited as a clinician value champion for their clinic. They will participate in twice monthly clinician value champion training webinars for six months and then launch a 12-month initiative within their clinic to reduce PIM prescribing among PLWD. Study outcomes will be assessed 12 months after they launch their initiative.

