Duration of Enrollment and Follow-up: Using Medicare claims data for our primary outcome, with a follow-up period of one year after completion of the 6-months of value champion training, and with medication possession rates calculated per patient each quarter, we will have approximately 4 MPR observations per patient or 8,000 observations per group for USMM analyses and 2,000 per group for Ochsner.

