#### **4.3 Study Enrollment Procedures**

##### Patient Subjects

We will partner with two ACOs with primary care clinic locations. Prior to random assignment, we will stratify all clinics/practices based on high versus low historic prescribing rates, with the cut-point for inclusion in the study based on the distribution of overall rates for all 3 therapeutic classes using data for 2019-2020. These clinics will be randomized 1:1 to either the intervention or control arms of the study. We will work closely with leadership in each ACO over months 1-3 of the study to recruit an appropriate clinician from each clinic in the intervention arm of the study to participate in the study. A total of 30 clinicians across the two ACOs will participate in the intervention, with 30 clinics in the control group without a clinician value champion.

We will request a waiver of informed consent and waiver of HIPAA authorization for including patient data in this study. The intervention will be embedded within the health care system at the clinic level as a training program for clinicians. No patients will be recruited into this study. Although data from human subjects are involved, no contact will ever be made with patients as this project involves the use of secondary data only. Attempting to obtain authorization or consent would not be feasible as this study will involve a study population of an estimated 5,000 patients. Consent and authorization of patients for enrollment in this study would create bias, generate prohibitive study costs rendering the study unfeasible, and produce results that would not be generalizable to other health care organizations. Furthermore, contacting 5,000 subjects for written consent would increase the only risk for patients - breach of confidentiality. We will ensure subjects' protection against risk by following the measures outlined in the section below.

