### **9.2 Sample Size and Randomization**

Our sampling plan anticipates enrolling at least 30 of the 39 practices in USMM and 26 of the 28 practices in Ochsner. Based on Medicare enrollments of 39,000 members in USMM with a 20 percent dementia rate in 2019, and 10,000 members in Ochsner with approximately 10 percent of members diagnosed with dementia in 2019, we should have

at least 2,000 patients per treatment group for USMM and 500 patients per treatment group for Ochsner. For our primary outcome, with a follow-up period of one year and with mediation possession rates calculated per patient each quarter, we will have approximately 4 MPR observations per patient or 8,000 observations per group for USMM analyses and 2,000 per group for Ochsner. Even after assuming significant correlation across time within patient and modest correlation between patients within a practice, which will reduce effective sample sizes by 20%, we should have the equivalent of 6,400 observations per treatment group for our USMM analyses and 1,600 observations per treatment group for Ochsner.

The expectation of our intervention is that for each medication class, it will produce clinically relevant decreases in mean possession rates of 10% of a standard deviation. If the effect size is this large for a medication class and using a 5% level of significance, our Ochsner sample (with effective size of at least 1,600 per group) will have 80% power to discern a significant difference, while our larger USMM sample (with effective size of at least 6,400 per group) will have almost 100% power. Indeed, our USMM sample will have 80% power to find a significant difference, even if the effect size is only 5% of a standard deviation

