#### 9.2.1 Treatment Assignment Procedures

The unit of randomization will be the primary care practice or team. We anticipate 32 out of 39 teams from USMM to meet eligibility and 26 out of 28 practices for Ochsner. Within each ACO, we will randomly select half of the practices for participation in the value champion training and the remaining practices will continue with care as usual. Prior to random assignment, we will stratify practices based on high versus low historic prescribing rates. We will select practices for randomization and inclusion using a cut-point based on the distribution of overall rates for all 3 therapeutic classes using data for 2019-2020. Once randomized, a clinician value champion will be recruited from each of the clinics randomized to the intervention arm of the study in partnership with the ACO leadership.

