#### 9.4.2 Secondary outcomes

As a secondary outcome, for Specific Aim #2, we will also assess the incidence of falls during the study window. Falls are difficult to monitor using claims data, but Min and colleagues have developed a method that IAC and Brandeis staff (Co-Investigator [name]) have helped test for ICD-10. We will use the most conservative definition that looks for the presence of fall ‘reason for visit’ code on ED, ambulatory, or inpatient visit as indicated by a clinician bill (Part B). Key covariates in all of our regression models will include age and sex, both derived from the Medicare beneficiary summary files, house at IAC.

For Specific Aim #3, the five important implementation outcomes: appropriateness, fidelity, feasibility, and penetration will be assessed by analyzing interviews with clinician value champions. The Clinician interviews will provide us with data we need to assess the implementation outcomes.

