### 9.5 Data Analyses

Following an intent-to-treat design, all Medicare beneficiaries meeting our dementia eligibility criteria will be included in the study, regardless of level of engagement with practice clinicians. Data analysis will begin with descriptive statistics, comparing the mix of patients at each practice including demographics, chronic conditions, and incident versus prevalent dementia. This will allow us to check for balance between treatment and control practices and inform subsequent modeling. To determine the impact of the intervention, we will construct hierarchical models with time period observations nested within patient. These models will be random effects or generalized estimating equations (GEE) with robust standard errors, and will be either linear, if original MPRs are used as outcome, or generalized linear, if transformation necessary. The key variable of interest in these models will be the treatment indicator (assigned based on practice). Since there could well be a time effect of treatment, we will explore several model specifications, such as discrete indicators for the time periods or a single continuous variable. Interactions of treatment with time period will also be explored. By examining various different specifications involving time, we should be able to determine whether the intervention leads to a one-time change, a gradual trend over time, or a combination of both (an immediate jump with a further change, as time passes). Finally, we will explore the impact of this intervention on health inequities by stratifying our primary analysis by race/ethnicity.

Specific to Aim #3: Current approaches to evaluating implementation outcomes are still nascent, with few measures that have validated psychometric properties. Conceptually, these measures are inter-dependent, and are connected with service outcomes, such as patient safety. We will use data collected from interviews with the Value Champions to conduct a thematic analysis of the five implementation outcomes using a deductive approach.

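### The adjustment set for the primary models is not prespecified: neither the randomisation stratum nor the patient's pre-intervention MPR is named, which may cost precision

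*Combined protocol and SAP*

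**What the plan says.** **Covariates.** Section 9.4.2 states: "Key covariates in all of our regression models will include age and sex". Sections 9.1 and 9.5 add the treatment indicator. Section 9.5 adds time-period terms and treatment-by-time interactions, in forms to be explored.

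**Route to further covariates.** Section 9.5 begins with a description of patient mix by practice (demographics, chronic conditions, incident versus prevalent dementia) and says: "This will allow us to check for balance between treatment and control practices and inform subsequent modeling".

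**Stratification.** Section 9.2.1 says that before assignment "we will stratify practices based on high versus low historic prescribing rates". The next sentence gives the cut-point a second role: "We will select practices for randomization and inclusion using a cut-point based on the distribution of overall rates". The Précis ("with the cut-point for including a clinic in the study based on the distribution of overall rates") and Section 4.3 ("with the cut-point for inclusion in the study based on the distribution of overall rates") also tie it to inclusion, as does the Randomization text in Section 3.

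**Outcome data counted.** Section 3 describes MPRs "with a follow-up period of one year after completion of the 6-months of value champion training", and Section 9.2 says "we will have approximately 4 MPR observations per patient". Section 6.2.2 gives baseline assessments as not applicable.

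**Earlier claims.** Section 6 uses existing claims to select clinics, and the stratification uses 2019-2020 prescribing rates.

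**The concern.** The stratum was thought important enough to restrict the randomisation, and a patient's own earlier MPR is likely to be a strong predictor of later MPR. Neither is a stated model term.

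Three things are at stake.

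- **Precision.** Variation that these terms would explain stays in the residual.
- **Calibration.** Stratified randomisation removes between-stratum variation from the treatment contrast. A model without the stratum still counts that variation in the standard error, so a test that accounts for practice becomes conservative if the stratum is prognostic.
- **Prespecification.** The adjustment set can be settled after the arms have been compared on patient mix. The model family, the MPR transformation and the time specification are also open, so this adds one more choice made with data in view.

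**Working it through.** **1. The plan's own figure.** Two-sided 5%, normal approximation, SD 1: power = Φ(d/√(2/n) − 1.96).

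- Ochsner, n = 1,600 effective observations per arm, d = 0.10: 80.7% (plan: 80%).
- USMM, n = 6,400: 99.99% at d = 0.10 (plan: almost 100%) and 80.7% at d = 0.05 (plan: 80%).

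The figures reproduce, and no covariate enters them.

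**2. Inputs for the illustration.** From Section 9.2: 500 patients per arm (Ochsner) and 2,000 (USMM), 4 quarters, effect 0.10 SD. Practices per arm: 13 for Ochsner (26 practices). USMM has 15 from Section 9.2 (30 practices) or 16 from Section 9.2.1 (32). Assumed, because the documents give no values: practice ICC, within-patient correlation rho, correlation r of baseline with follow-up MPR, and the gap in mean MPR between high and low strata. Practice clustering is taken as modelled. Sections 9.1 and 9.5 nest observations only within patient, which is a separate matter.

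**3. Baseline MPR.** Variance of an arm mean:

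V = ICC/k + [(rho − ICC) + (1 − rho)/4]/n

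Power comes from the noncentral t with 2k − 2 df and noncentrality 0.1/√(2V). The lower bound multiplies only the second term by (1 − r²), so only patient-level variance falls. The upper bound multiplies all of V.

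Ochsner, ICC 0.01, rho 0.5: V = 0.01/13 + 0.615/500 = 0.000769 + 0.001230 = 0.001999. Noncentrality 1.58, 24 df, power 33.0%.

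USMM, k = 15: V = 0.01/15 + 0.615/2,000 = 0.000667 + 0.000308 = 0.000974. Noncentrality 2.27, 28 df, power 59.0%.

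| ICC 0.01, rho 0.5 | Unadjusted | r = 0.3 | r = 0.5 | r = 0.7 |
|---|---|---|---|---|
| Ochsner (13 per arm) | 33.0% | 34.6-35.6% | 37.9-41.8% | 44.3-56.6% |
| USMM (15 per arm) | 59.0% | 60.2-63.0% | 62.5-71.4% | 66.2-86.5% |
| USMM (16 per arm) | 61.1% | 62.4-65.1% | 64.8-73.5% | 68.7-88.0% |

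At ICC 0.05 and r = 0.7, Ochsner goes from 16.1% to 17.5-27.0% and USMM (15 per arm) from 20.6% to 21.2-35.6%. The lower-bound gain is then under 1.5 points in both.

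**4. Low end.** If the plan's 20% cut were all within-patient correlation, 1 + 3·rho = 1/0.8 = 1.25, so rho = 0.083. An exchangeable correlation then implies r = 0.15 with one baseline quarter and 0.27 with four. Ochsner at ICC 0.01: V = 0.000769 + 0.3025/500 = 0.001374, power 44.9%. It rises to 45.2-45.7% at r = 0.15 and 46.4-48.4% at r = 0.3. On the plan's own calculation without clustering, 80.7% rises to 81.6% (one quarter) or 83.5% (four).

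**5. Stratum term.** Simulated practice means with variance ICC + 0.615/m at ICC 0.01 (m = 38.5 Ochsner, 125 USMM), randomised half and half within strata (12 high and 14 low; 16 and 16). Regression on treatment without and with the stratum, t test, effect 0.10 SD. Results at ICC 0.01:

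| Gap between strata | Ochsner power without term (33% with) | USMM power without term (61% with) |
|---|---|---|
| 0 | 33% | 61% |
| 0.05 SD | 32% | 59-60% |
| 0.1 SD | 29.5% | 54.6% |
| 0.2 SD | 20.9% | 37.2% |

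Without the term, type I error is 4.1% (Ochsner) and 3.4% (USMM) at 0.1 SD, and 2.1% and 1.1% at 0.2 SD. With it, the error is 5%. At ICC 0.05 and gaps of 0.1 or 0.2 SD, power without the term is 15.1% or 12.7% against 16.0% for Ochsner, and 20.3% or 16.8% against 21.6% for USMM. The gains in steps 3 and 5 overlap and must not be added.

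**The case against.** **The terms are not excluded.** A reader might infer that the stratum and baseline MPR are ruled out. The wording of Section 9.4.2 is an open list, so they are only not prespecified. Section 9.5 also does not say outright that its time periods are follow-up quarters only, and it looks for an immediate jump. Pre-intervention quarters could therefore be meant, although the observation counts in Sections 3 and 9.2 cover only the follow-up year. This objection stands and limits the claim to prespecification.

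**Outcomes are not compared first.** A reader might also infer that covariates are picked after seeing results. The listed comparison covers demographics, chronic conditions and dementia type. The choice would be data-driven, but not outcome-driven on the stated text.

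**The gain may be small.** This also stands. It is small at low r, at low rho, or at ICC 0.05 if only patient-level variance falls. Stratum gaps of 0.1 and 0.2 SD equal and double the whole treatment effect. The stratum uses overall rates across all three classes while the outcomes are class-specific, so its link to any one class is unknown. If the cut-point restricts entry, included practices may vary little on it.

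**Baseline may be missing.** Section 4.1 requires Part D coverage only during the intervention year, and Section 10.1 describes an inception cohort. Some patients may have no usable earlier MPR.

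**Demonstration trial.** Section 9.1 describes the funding as a feasibility and acceptability demonstration. That lowers the priority, but Section 9.1 also states a comparative hypothesis for each class.

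**Conclusion.** The point holds as a gap in prespecification with a possible loss of precision. The plan commits to age, sex, treatment and time. It does not commit to the stratification factor or to a baseline value that the same claims source could supply, and it lets a comparison of the arms on patient mix inform the model.

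It would be tempting to call the treatment estimate biased or the analysis invalid. The documents do not support that for this omission. If the cohort is fixed before the intervention, as the Précis and Section 9.1 say, the randomised comparison is unbiased with or without these terms. That statement is conditional, because Sections 3 and 4.1 set eligibility during the intervention year, after randomisation. Any bias from that would be a separate problem that these covariates are not meant to cure.

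No single figure for the gain can be drawn from the documents. Over the assumed ranges, the Ochsner gain from baseline MPR at ICC 0.01 runs from under half a point (rho 0.083, r 0.15) to about 24 points (rho 0.5, r 0.7, practice variance also explained). The stratum gain runs from nil to about 12 points for Ochsner and 24 for USMM. All of this presumes that practice clustering is modelled. The unadjusted power levels belong to the clustering question and are not a consequence of this one.

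**What to change.** In Section 9.5, before outcome data are opened, name one primary model per medication class, within whichever model accounts for practice clustering. Its terms should be:

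- treatment and quarter;
- the high/low prescribing stratum as used in randomisation, if included practices vary on it;
- ACO, if the two are pooled;
- age and sex;
- the patient's class-specific MPR averaged over available quarters before champion training, with an indicator for patients who have none.

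State that the balance table is descriptive and does not select covariates, and that any other adjustment is a sensitivity analysis.

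Three texts need reconciling first, so that stratum variation and baseline availability are known:

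- whether the prescribing cut-point restricts practice entry or only defines strata (Précis and Sections 3, 4.3 and 9.2.1);
- whether patient eligibility is set before the intervention (Précis, Section 9.1) or during the intervention year (Sections 3 and 4.1);
- what the inception-cohort description in Section 10.1 means for who has earlier data.

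The cost is the SAP wording, one patient-level pre-period extract from the same claims source, a missing-baseline rule, and one practice-level degree of freedom for the stratum.

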### 9.5 Data Analyses

Following an intent-to-treat design, all Medicare beneficiaries meeting our dementia eligibility criteria will be included in the study, regardless of level of engagement with practice clinicians. Data analysis will begin with descriptive statistics, comparing the mix of patients at each practice including demographics, chronic conditions, and incident versus prevalent dementia. This will allow us to check for balance between treatment and control practices and inform subsequent modeling. To determine the impact of the intervention, we will construct hierarchical models with time period observations nested within patient. These models will be random effects or generalized estimating equations (GEE) with robust standard errors, and will be either linear, if original MPRs are used as outcome, or generalized linear, if transformation necessary. The key variable of interest in these models will be the treatment indicator (assigned based on practice). Since there could well be a time effect of treatment, we will explore several model specifications, such as discrete indicators for the time periods or a single continuous variable. Interactions of treatment with time period will also be explored. By examining various different specifications involving time, we should be able to determine whether the intervention leads to a one-time change, a gradual trend over time, or a combination of both (an immediate jump with a further change, as time passes). Finally, we will explore the impact of this intervention on health inequities by stratifying our primary analysis by race/ethnicity.

Specific to Aim #3: Current approaches to evaluating implementation outcomes are still nascent, with few measures that have validated psychometric properties. Conceptually, these measures are inter-dependent, and are connected with service outcomes, such as patient safety. We will use data collected from interviews with the Value Champions to conduct a thematic analysis of the five implementation outcomes using a deductive approach.

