## **9 STATISTICAL CONSIDERATIONS**

### **9.1 General Design Issues**

Our hypothesis is that for each medication class, the intervention will produce clinically relevant decreases in mean possession rates of 10% of a standard deviation in patients seen in intervention clinics compared to those who are seen in control group clinics.

The study design was chosen to meet the requirements of the funder for a non-pharmacologic/non-device intervention for people living with dementia, conducted in a health system setting. The 24-months of funding is for a demonstration project, intended to demonstrate the feasibility and acceptability of the intervention, but with the stipulation by the funder that the trial must be a randomized controlled trial, one with a control group. In response, we proposed a cluster-randomized trial where the intervention will be randomized at the primary care clinic level, not the patient level, and existing health systems claims data will be used to address our primary outcome (Specific Aim #1) and one of our secondary outcomes: Specific Aim #2: emergency department visits and hospitalizations for a fall.

The primary outcome measure for this study will be medication possession rates (MPR) per quarter, for the 3 therapeutic classes of medications - antipsychotics, benzodiazepines, and hypoglycemics - that are considered low-value for beneficiaries with dementia. Unlike many studies using medication possession rates to exam adherence, we are interested in reducing, not increasing, the percent of days covered. Following an intent-to-treat design, claims data from all Medicare beneficiaries meeting our dementia eligibility criteria prior to the start of the value champion intervention will be included in the analysis. To determine the impact of the intervention, we will construct hierarchical models with time period observations nested within patient. These models will be random effects or generalized estimating equations (GEE) with robust standard errors, and will be either linear, if original MPRs are used as outcome, or generalized linear, if transformation necessary. The key variable of interest in these models will be the treatment indicator (assigned based on practice randomization to intervention or control group).

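### The primary model has no practice level although practices are randomised; with the patient as top level, the treatment standard error is too small for any positive practice ICC

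*Combined protocol and SAP*

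**What the plan says.** Section 9.2.1 is clear about allocation: "The unit of randomization will be the primary care practice or team". It adds that, before assignment, "we will stratify practices based on high versus low historic prescribing rates".

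The primary analysis is described twice, in sections 9.1 and 9.5. Section 9.5 reads "To determine the impact of the intervention, we will construct hierarchical models with time period observations nested within patient", and section 9.1 likewise says "we will construct hierarchical models with time period observations nested within patient". Both stop at the patient. On estimation, section 9.5 says "These models will be random effects or generalized estimating equations (GEE) with robust standard errors" and does not say what the robust errors are clustered on. In the outcome modelling, practice appears only as the basis for the treatment indicator. Its other appearance in section 9.5 is a descriptive comparison of patient mix.

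On covariates, section 9.4.2 says "Key covariates in all of our regression models will include age and sex"; the randomisation stratum is not mentioned.

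Section 9.2 does recognise clustering when sizing the trial. It allows for within-patient correlation over time and for "modest correlation between patients within a practice, which will reduce effective sample sizes by 20" percent. It gives no ICC.

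**The concern.** Patients in one practice share prescribers, and the trial stratifies on historic prescribing because practices are expected to differ. Two arms of 13 to 16 practices will therefore differ somewhat by chance. A model whose highest level is the patient cannot see that variation. It averages it over hundreds or thousands of patients as if each had been assigned separately.

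Robust errors clustered on the patient do not help, because they protect only against correlation between quarters within a patient. A random-effects model with a patient intercept alone has the same gap.

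At stake is the primary test. Confidence intervals would be too narrow, and a chance difference between practices could be reported as an effect of the value champion. The exposure is greater in USMM, whose practices hold more patients.

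**Working it through.** **Inputs from the documents.** Section 9.2: 500 patients per arm in Ochsner and 2,000 in USMM; 4 quarterly MPR values per patient; effect 0.1 SD; 5% significance. Section 9.2.1: 26 Ochsner practices and 32 USMM teams, split in half. This gives k = 13 per arm with m = 500/13 = 38.5 patients each (Ochsner), and k = 16 with m = 2,000/16 = 125 (USMM).

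**Assumptions.** Practice ICC 0.001 to 0.05; within-patient correlation rho = 0.7 (0.5 and 0.9 as sensitivity); equal practice sizes; practice effects constant over quarters; total SD 1. The documents give neither correlation.

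**Step 1: the plan's own power.** The 20% reduction gives 0.8 × 2,000 = 1,600 and 0.8 × 8,000 = 6,400 effective observations per arm. With two-sided 5%, power = Phi(d/sqrt(2/n) − 1.96):
- n = 1,600, d = 0.10: 80.7%
- n = 6,400, d = 0.10: 99.99%
- n = 6,400, d = 0.05: 80.7%

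These match the stated figures.

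**Step 2: variance of an arm mean.**
- Patient as top level: V_pt = [rho + (1 − rho)/4]/(km)
- With the practice level: V_true = ICC/k + (rho − ICC)/(km) + (1 − rho)/(4km)
- Difference: V_true − V_pt = ICC(m − 1)/(km), which is positive whenever ICC > 0 and m > 1

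At rho = 0.7 and ICC = 0.01:
- Ochsner: V_pt = 0.775/500 = 0.001550; V_true = 0.001550 + 0.01 × 37.46/500 = 0.002299; ratio 1.48
- USMM: V_pt = 0.775/2,000 = 0.0003875; V_true = 0.0003875 + 0.01 × 124/2,000 = 0.0010075; ratio 2.60

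**Step 3: real type I error of a nominal 5% test**, 2[1 − Phi(1.96/sqrt(V_true/V_pt))], at rho = 0.7, without stratification:

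| ICC | Ochsner | USMM |
|---|---|---|
| 0.001 | 5.6% | 6.9% |
| 0.005 | 7.9% | 14% |
| 0.01 | 11% | 22% |
| 0.02 | 16% | 34% |
| 0.05 | 29% | 51% |

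At ICC 0.01, rho = 0.5 gives 12% and 26%; rho = 0.9 gives 10% and 20%.

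**Step 4: effect of stratified randomisation.** Simulated practice means, 8,000 null trials per cell, rho = 0.7, median-split strata, with an assumed correlation r between historic rate and practice effect. Type I error of the patient-level test for r = 0.5 / 0.7 / 0.9:
- ICC 0.01: Ochsner 9.8 / 9.3 / 8.4%; USMM 20.2 / 17.6 / 14.1%
- ICC 0.05: Ochsner 26.0 / 23.8 / 20.2%; USMM 48.0 / 44.0 / 38.0%

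A practice-level t-test with the stratum as covariate held 4.6–5.2% in every stratified cell. Without the stratum it was conservative (USMM, ICC 0.01: 3.5 / 3.0 / 1.9%).

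**Step 5: the small-sample correction.** In a further simulation (4,000 runs per setting, no strata, rho = 0.8, 13 Ochsner and 15 USMM practices per arm, ICC 0 to 0.05), practice-clustered robust errors with a normal reference rejected 6.4–7.8% of the time. With a K/(K − 1) correction and a t reference on practices minus 2, the rate was 4.4–5.8%.

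**The case against.** The best reply is that the wording permits a practice-clustered sandwich. The authors plainly know of within-practice correlation, so this may be under-specification and not a decision to ignore it. Practice clustering would indeed remove the first-order understatement. But the only grouping that the stated hierarchy supplies is the patient, and an analyst following sections 9.1 and 9.5 would stop there. Even with practice clustering, a plan with about 26 and 32 practices needs a small-sample rule, and none is given.

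A second reply is that the size is assumed. That stands. The plan's one anchor is its 20% allowance, a variance ratio of 1/0.8 = 1.25. If all of that were practice clustering, the patient-level test would have a type I error of 2[1 − Phi(1.96/sqrt(1.25))] = 8.0%. The larger figures above need more clustering than the plan allowed for. The direction does not depend on the ICC chosen.

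Third, the covariate list is open-ended, and leaving out the stratum alone makes a practice-level test conservative. That also stands: the stratum term is there to recover precision, not to prevent false positives.

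**Conclusion.** The concern holds. Followed as written, with the patient as top level, the primary model understates the treatment standard error for every positive practice ICC. The harm is slight at ICC 0.001. At ICC 0.01 it is serious: roughly twice the nominal error rate in Ochsner, and three to four times in USMM, after allowing for stratified randomisation. The direction is certain; the size rests on the assumed ICC, within-patient correlation, equal practice sizes and constant practice effects. The figures apply to MPR on its original scale; inflation was not computed for falls or prescription counts. Because this is the primary test of a cluster-randomised trial, the plan must be corrected before the analysis.

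**What to change.** In sections 9.1 and 9.5, specify quarters within patients within practices, with the high/low historic-prescribing stratum as a covariate, plus ACO if the two organisations are pooled.

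- For linear MPR models: practice and patient random intercepts with Kenward-Roger or Satterthwaite degrees of freedom.
- As an alternative for linear models, and for transformed or ordinal MPR: GEE with the practice as cluster, a small-sample-corrected sandwich and a t reference based on the number of practices. The same form suits falls and prescription counts.

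The cost is a few sentences, one model level and a stratum term; no new data. Intervals will widen and section 9.2 must restate power. For 0.1 SD at rho = 0.7, a practice-level t-test on 2(k − 1) degrees of freedom, before any gain from the stratum, has about 39% (Ochsner) and 90% (USMM) power at ICC 0.001, and 29% and 58% at ICC 0.01. The plan states 80% and almost 100%.

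Not all of that gap is the price of this change. With ICC zero and the patient-level model, power at rho = 0.7 is already Phi(0.1/sqrt(2 × 0.001550) − 1.96) = 43% in Ochsner and Phi(0.1/sqrt(2 × 0.0003875) − 1.96) = 95% in USMM. Most of the Ochsner shortfall therefore comes from the assumed within-patient correlation, which the 20% allowance does not cover.
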